#### **4.3.1.4. Supplementary estimand for secondary endpoint analyses**

A supplementary estimand analyses for secondary endpoints will be performed if **CCI** of participants in the ITT analysis set are unable to take  $\geq 80\%$  doses of gepotidacin up to each of 24 hours  $\pm 4$ , 48 hours ( $\pm 4$  hours), 72 hours ( $\pm 4$  hours), and 96 hours ( $\pm 4$  hours). The supplementary estimand analysis will be performed using ITT analysis set. Participants who are unable to complete the CSS assessment at each timepoint (24 hours  $\pm 4$ , 48 hours ( $\pm 4$  hours), 72 hours ( $\pm 4$  hours), and 96 hours ( $\pm 4$  hours)) will be considered treatment failures and included in the analysis as not improved or not resolved for clinical symptom resolution.

Counts and percentage of participants with clinical symptom improvement and resolution at each timepoint and its corresponding 95% Exact Binomial CIs will be presented.

#### **4.3.1.5. Sensitivity analyses of supplementary estimand for secondary endpoints**

Sensitivity of supplementary estimands analyses for secondary endpoints will be performed according to rule mentioned in Section 4.3.1.4. considering ITT analysis set. Multiple imputation method will be used to impute the missing outcome at each timepoint (24 hours  $\pm 4$ , 48 hours  $\pm 4$  hours, 72 hours  $\pm 4$  hours and 96 hours  $\pm 4$  hours) as described in Section 4.2.3 for clinical symptom improvement and resolution, respectively.

[figure not shown]
Counts and percentage of participants with “Clinical improvement with resolution outcome” at each timepoint and its corresponding 95% (Wald) CIs will be presented.

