Objectives, endpoints, and estimands: The primary objective of this study is to evaluate the clinical symptom improvement with gepotidacin treatment in female participants with uUTI at (24 hours [± 4 hours]). This will be evaluated by the number of participants who achieve clinical symptom improvement (without the need for other systemic antimicrobials), defined as a decrease from Baseline in CSS total score of at least 1 point at (24 hours [± 4 hours]). For additional information on the primary, secondary, and exploratory objectives and endpoints, refer to Section 3.

[figure not shown]
Overall design: This is a Phase 3b, open-label, single-arm, multicenter study to evaluate clinical symptom improvement and the safety of gepotidacin in female participants ≥ 12 years of age with clinical symptoms and urine dipstick findings suggestive of uUTI. Participants who meet eligibility requirements will receive gepotidacin 1500 mg administered orally as 2×750 mg tablets BID for 5 days. (Note: Each dose is to be taken after food consumption and with water to assist with tolerability.) Clinical symptom and safety assessments will be conducted throughout the study. The total duration of study participation is approximately 28 days, with at least 1 planned on site study visit and 6 telephone call study contacts (see Section 1.3 and Section 8 for study visit details), with allowance for unscheduled visits. For additional information on the overall design, refer to Section 4.1.

Number of participants: Approximately 90 participants will be enrolled in the study to ensure at least 82 evaluable participants are included in the primary analysis, such that the half width of the 95% CI is approximately $\leq 10\%$, under an assumption that 74% of participants meet the primary endpoint criteria as observed in the Phase 3 studies.

Data monitoring/other committee: This will be overseen by the GSK SRT (Section 10.9.6).

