#### **4.1.1. General Methodology**

Participants who prematurely withdrew from study will not be replaced.

Continuous data will be summarized using descriptive statistics: n, mean, standard deviation (std), median, minimum, and maximum. Categorical data will be summarized as the number and percentage of participants in each category.

Unless stated otherwise, confidence intervals (CI) will be produced using 95% confidence levels.

[figure not shown]

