#### 4.2.3. Sensitivity analyses for primary endpoint analysis

Sensitivity analysis will be conducted to examine the robustness of the primary efficacy results for the primary estimand. The sensitivity analysis will be performed using the CE24 set. A sensitivity analysis for the primary endpoint will be carried out to assess the impact for those participants who are unable to complete the CSS assessment at 24 hours ( $\pm$ 4 hours). Missing clinical improvement data (without any antibiotic use) will be imputed under the missing at random (MAR) assumption. If an antibiotic is taken for uUTI before or at the timepoint of CSS assessment and/or for other infections before the timepoint of CSS assessment, the outcome variable will be imputed as (“Participants without Clinical Improvement or Resolution”). Multiple imputation method will be implemented to impute the incomplete (missing) CSS at 24 hours ( $\pm$ 4 hours) using following steps -

Step 1: The missing clinical improvement with resolution outcome (without any antibiotics use) will be imputed using a logistic regression model. The following baseline covariates will be included in the imputation model. The number of imputations will be 1000 and SEED=219575.

- CCI
- 
- 
- 

Any participants who have a missing value for one or more model covariates listed above will be excluded from the imputation model. The participants with missing covariates will be classified as “Participants without Clinical Improvement or Resolution.”

Model for multiple imputation will be diagnosed to ensure the good fit for the data of clinical response.

Step 2: Step 1 will generate 1000 imputed datasets. From the imputed dataset, participants with clinical improvement will then be derived using the imputed and non-missing data per Section 4.2.1. and [Table 1](#)

Step 3: The estimated quantities in Step 2 will be combined across the imputed datasets using Rubin’s rules to provide pooled estimates for the clinical symptom improvement rate.

Percentage of participants with “Clinical improvement with resolution outcome” at 24 hours  $\pm$  4 hours will be estimated and its corresponding 95% (Wald) CIs will also be presented.

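### SAP 4.3.1.5 puts untransformed Wald intervals on imputed response rates; if the true rates lie near 100% or 0%, limits leave the 0-100% range and coverage falls

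*SAP*

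**What the plan says.** SAP 4.3.1.5 is the sensitivity analysis for the supplementary estimands of the secondary endpoints. It is run "according to rule mentioned in Section 4.3.1.4. considering ITT analysis set". "Multiple imputation method will be used to impute the missing outcome at each timepoint", that is at 24, 48, 72 and 96 hours, for improvement and for resolution, following SAP 4.2.3. That section uses logistic imputation under missing at random, 1000 imputations and Rubin's rules. The percentages are then reported "at each timepoint and its corresponding 95% (Wald) CIs will be presented".

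The interval types around it differ:

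- SAP 4.3.1.4, the ITT analysis that 4.3.1.5 tests: exact binomial.
- SAP 4.3.1.2 (main secondary analysis) and 4.3.1.3 (its imputation analysis on the clinically evaluable sets): exact binomial.
- SAP 4.2.3, the imputation analysis of the primary endpoint: the 24-hour percentage "will be estimated and its corresponding 95% (Wald) CIs will also be presented".

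The general rule in SAP 4.1.1 fixes only the level: "confidence intervals (CI) will be produced using 95% confidence levels". No section states a transformation, a truncation or a rule for 0% or 100%.

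**The concern.** A Wald interval is symmetric about the estimate, and its width depends on p(1 - p), which vanishes at both ends of the scale. Near 100% or 0% it can give impossible limits and cover the true rate too rarely.

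The only response rate in the documents is the 74% assumed for 24-hour improvement, where Wald limits behave well. SAP 4.3.1.5 applies the same interval to improvement as late as 96 hours. Improvement is any fall of at least 1 point on a 0-12 score, after several days of antibiotic. Imputing under missing at random, instead of counting missing scores as failures, also tends to raise that rate. If the sentence covers resolution as well, it applies to a total score of 0 as early as 24 hours, which may be rare. At stake are limits above 100% or below 0% in the study report, and a sensitivity interval whose method differs from that of the analysis beside it.

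**Working it through.** **Inputs.** Two-sided 95%, z = 1.96 (SAP 4.1.1). Sample size from Protocol 1.1: "Approximately 90 participants will be enrolled in the study to ensure at least 82 evaluable participants are included in the primary analysis". The ITT set used in 4.3.1.5 is therefore taken as n = 90. Planning rate: 74% ("under an assumption that 74% of participants meet the primary endpoint criteria"). Assumptions, because the documents give no figure: true rates from 74% to 99% (1% to 26% is the mirror image) and 5% or 10% of outcomes missing.

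**The plan's own figure.** Protocol 1.1 sizes the study "such that the half width of the 95% CI is approximately" at most 10 points. At p = 0.74, the Clopper-Pearson half-width is 9.97 points at n = 82 and 10.03 at n = 81. The Wald half-width at n = 82 is 1.96 × √(0.74 × 0.26/82) = 9.49 points. The planned size therefore agrees with exact limits, and at 74% the two methods differ little.

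**Where Wald limits leave the range.** With complete data the upper limit p + 1.96√(p(1 - p)/n) exceeds 1 when p > n/(n + 1.96²) = 90/93.84 = 95.9%. In counts:

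| Responders | Wald | Clopper-Pearson | Wilson |
|---|---|---|---|
| 86/90 | 91.3-99.8% | 89.0-98.8% | 89.1-98.3% |
| 87/90 | 93.0-100.4% | 90.6-99.3% | 90.7-98.9% |
| 88/90 | 94.7-100.8% | 92.2-99.7% | 92.3-99.4% |
| 90/90 | 100-100% | 96.0-100% | 95.9-100% |

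**Complete-data Wald coverage at n = 90** (exact enumeration): 0.939 at 74%, 0.946 at 90%, 0.938 at 95%, 0.930 at 97%, 0.835 at 98%, 0.595 at 99%.

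**After imputation.** The planned analysis pools imputed datasets, so it was simulated: n = 90, outcomes missing completely at random, intercept-only imputation, 200 imputations, Rubin's rules, 20,000 replicates. With q the pooled rate, U the mean within-imputation variance and B the between-imputation variance, the total variance is T = U + (1 + 1/m)B. The Wald limits are q ± t√T. Entries are for 5% / 10% missing.

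| True rate | Wald coverage | Limit outside 0-100% | Zero width | Wilson-type coverage |
|---|---|---|---|---|
| 74% | 0.945 / 0.942 | 0 / 0 | 0 / 0 | 0.952 / 0.949 |
| 90% | 0.925 / 0.919 | 0.022 / 0.034 | 0 / 0 | 0.951 / 0.956 |
| 95% | 0.923 / 0.909 | 0.380 / 0.418 | 0.001 / 0 | 0.966 / 0.959 |
| 97% | 0.922 / 0.916 | 0.747 / 0.772 | 0.003 / 0 | 0.957 / 0.964 |
| 99% | 0.577 / 0.629 | 0.969 / 0.990 | 0.020 / 0.001 | 0.945 / 0.953 |

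At 98% Wald coverage is 0.79 to 0.82. Repeated runs move the entries by about 0.01. Imputation makes zero width rare, but it does not cure the overshoot or the loss of coverage from 98% upward.

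**Wilson-type interval used above.** With r = (1 + 1/m)B/U (0 if U = 0) and a = 1.96²(1 + r)/n, the limits are [2q + a ± √(a² + 4a·q(1 - q))] / [2(1 + a)]. They stay within 0-100%. If every imputed dataset is at 100%, the lower limit is 1/(1 + a) = 1/(1 + 3.84/90) = 95.9%.

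**The case against.** The strongest reply is that this is peripheral and conditional. SAP 4.3.1.5 follows the rule of 4.3.1.4, which operates only if a redacted share of the ITT set is below 80% compliance. No hypothesis is tested, and the late timepoints already have exact intervals in 4.3.1.2, 4.3.1.3 and 4.3.1.4. A Wald interval after Rubin's rules is a standard default. The extreme rates are also assumed: 98% of 90 means about two failures. Antimicrobial users count as failures, as do participants with missing imputation covariates, which pulls rates away from 100%. All of this stands, and it limits the weight of the point. It does not make the interval sound if the rates do turn out extreme.

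Four stronger readings are tempting, and the documents do not support them.

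- That the analysis cannot show robustness. Robustness is judged mainly by the shift in the point estimate between missing-as-failure and imputed, which the interval formula does not alter. Being narrower than the exact interval is no fault in itself: Clopper-Pearson over-covers here (0.976 to 0.990 at 95-99%, complete data).
- That intervals will collapse to zero width. This needs every imputed dataset at exactly 0% or 100%, which occurred in at most 2% of simulated trials with 5-10% missing.
- That SAP 4.2.3 is defective for the same reason. It concerns 24-hour improvement, planned at 74%, where Wald coverage is about 0.94 with no overshoot.
- That resolution is certainly included. The Wald sentence names only the improvement-with-resolution outcome, the SAP's label for the improvement endpoint. Resolution is the natural reading, since the same section imputes it and 24 hours is a secondary timepoint for resolution alone, but it remains an inference.

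**Conclusion.** The point holds as an optional refinement. SAP 4.3.1.5 specifies an interval that is adequate at mid-range rates and poor near the ends of the scale, and it differs from the exact interval of the analysis it supports.

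Whether this matters depends on rates that the documents do not give. If the true rate is 95% or more (or 5% or less for resolution, if covered), impossible limits are common: about 37-43% of trials at 95% and 75-77% at 97%. Coverage suffers seriously only further out, at about 0.79-0.82 at 98% and 0.57-0.63 at 99%. Between 90% and 97% it is about 0.91-0.93.

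These figures assume n = 90, 5-10% missing completely at random and an imputation model without covariates; the SAP's own covariates are redacted. Neither the primary result nor the sample size is affected.

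**What to change.** In SAP 4.3.1.5, replace the Wald interval with a Wilson-type interval for multiply imputed proportions, computed from the Rubin-pooled estimate and total variance and defined at 0% and 100%. State that it applies to both improvement and resolution at each timepoint. In the simulations it covered about 0.945 to 0.97 at true rates from 74% to 99%, so nothing is lost at mid-range rates.

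Two alternatives are worse. Pooling logits computed in each imputed dataset is undefined whenever any one of them is at 0% or 100%; some but not all were at 100% in about 17-45% of simulated trials at true rates of 98-99%. Copying the exact binomial wording from 4.3.1.3 is incomplete, because a pooled count is generally not a whole number.

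The same change in 4.2.3 is optional, for consistency only. The cost is one SAP sentence and a small code change.

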### **4.3.2. Supportive secondary endpoint**

No supportive secondary endpoint analysis will be performed.

## **4.4. Exploratory Analyses**

[figure not shown]
**CCI**

[figure not shown]
**CONFIDENTIAL**

219575

CCI

CCI

CCI

CCI

## 4.5. Safety Analyses

The safety analyses will be based on the safety analysis set.

### 4.5.1. Extent of Exposure

Treatment exposure will be summarized for gepotidacin treatment using the safety and CE24 analysis set. Duration of treatment (days), the number of doses administered, number of tablets, average daily dose and cumulative actual dose will be presented in treatment exposure summary. Dose administration and exposure data for all participants will be generated in the listing. Additionally, a separate table will be created for ICEs, summarizing the participants who did not adhere to two doses before the 24 hours ( $\pm 4$  hours) CSS assessment, and indicating whether the compliance was above or below 80% at 48 hours ( $\pm 4$  hours), 72 hours ( $\pm 4$  hours), 96 hours ( $\pm 4$  hours) assessment.

#### 4.5.2. Adverse Events

The severity of TEAEs and treatment-emergent SAEs will be determined by the investigator according to the US National Institute of Allergy and Infectious Diseases [DAIDS, 2017] Table for grading the severity of adult and pediatric AEs. All reported TEAEs will be coded using standard Medical Dictionary for Regulatory Affairs (MedDRA) version 27.0 or later depending on the time of reporting and summarized by system organ class (SOC) and preferred term (PT).

A treatment emergent adverse event (TEAE) is defined as an adverse event (AE) with start date/time after the first dose date/time of the study treatment. If the time part is missing, dates will be considered and if date and time both are missing then eCRF question on whether the Adverse Event (AE) occurred before, after, or on the same day as the study intervention will be considered. Only TEAE will be included in summary tables, but all AEs will be displayed in detailed subject listings.

AEs will be summarized as the following:

- AEs by SOC, PT and maximum grade
- Serious adverse event (SAE) by SOC, PT and Maximum grade,
- Non-Serious adverse event (Non-SAE) by SOC and PT
- Drug-related adverse event (AE) by SOC, PT and Maximum grade,
- Drug-related non-serious adverse event by overall frequency,
- Drug-related fatal and non-fatal serious adverse event (SAE),
- Common AEs
- Adverse event (AE) leading to discontinuation of study intervention,
- Adverse event (AE) leading to withdrawal from study,
- Adverse events of special interests (AESIs) by SOC, PT and Maximum grade.
- Summary of deaths

**AEs, SAEs and Non-SAEs by SOC, PT and Severity grade:** Summary (counts & percentages) of adverse events (AEs), serious adverse events (SAE) and non-serious adverse events (non-SAEs) will be produced by system organ class (SOC), preferred term (PT). All adverse events (AEs) listing will be displayed at participant level in detail. Summary for serious adverse events (SAEs) will be summarised by System Organ Class, Preferred Term, and severity grade.

Adverse event severity is categorised as grade 1 (mild), grade 2 (moderate), grade 3 (severe), grade 4 (potentially life threatening) and grade 5 (death). Adverse events starting after the first dose of study treatment with a missing severity will be classified as severe. If a participant reports an AE more than once within an SOC/PT, the AE with the worst-case (maximum) severity will be used in the corresponding severity summaries. A Summary table for adverse events leading to permanent discontinuation of study

treatment or withdrawal from study by system organ class (SOC) and preferred term (PT) and maximum grade will be generated.

**Common AEs:** A summary of (counts & percentages) of common AEs with incidence $\geq 2\%$  (before rounding) will be produced in descending order of the total incidence of PT.

**Common Non-SAEs:** A Summary of Common (CCI) Non-Serious Adverse Events by System Organ Class and Preferred Term will be produced.

**AEs and SAEs related to study intervention:** Relationship to gepotidacin, as indicated by the investigator, is classified as “not related” or “related”. Adverse events with a missing relationship to gepotidacin will be recorded as “related” to study treatment. If a participant reports the same AE more than once within an SOC/PT, the AE with the worst-case relationship to gepotidacin will be used in the corresponding relationship summaries. Summary tables for drug-related adverse events (AEs) will be generated by system organ class (SOC), preferred term (PT) and maximum severity grade. The summary for drug-related non-serious adverse events and serious adverse events (SAEs) (fatal and non-fatal) will also be produced by preferred term (PT)

Adverse events analyses including the analysis of AEs, SAEs and other significant AEs will be based on GSK Core Data Standards.

All AEs will be listed.

A Summary of deaths will be provided and participants profile for death will also be listed using enrolled analysis set.

In summary tables, system organ classes (SOCs) will be sorted in descending order of the total incidence then alphabetically, preferred terms (PTs) will be sorted in descending order of the total incidence then alphabetically within the SOC.

For completely missing or partial missing AE start date or end date, imputation rules will be applied following Appendix Section [6.3.8](#).

Details of the planned displays for AEs and SAEs are provided in Output programming specifications (OPS) and will be based on GSK Data Standards and statistical principles.

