### 6.3.4 Treatment Emergent Flag for Adverse Events

Flag	Definition
Treatment Emergent	If adverse event (AE) onset date/time is on or after treatment start date/time, i.e., study intervention starts date/time $\leq$ adverse event (AE) starts date/time. If time is missing, only date will be compared.

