	
 
 Missing start day	 
If study intervention start date is missing (i.e., participant did not start study intervention), then set start date = 1st of month.
 
Else if study intervention start date is not missing:
 
 
If month and year of start date = month and year of study intervention start date, then 
 
If stop date contains a full date and stop date is earlier than study intervention start date, then set start date= 1st of month.
 
Else set start date = study intervention start date.
 
 
 
 
Else set start date = 1st of month.
 
In this case, event is considered On-treatment and treatment emergent as per Section 6.3.4.
 	
 
 Missing start time	 
Midnight 0:00:00 will be used for AEs with missing start time to determine if it's AChE-I
 
 
Treatment start time will be used for AEs with missing start time if treatment start date is same as AEs start date.
 
 	
 
 	 
If study intervention start date is missing (i.e. participant did not start study intervention), then set start date = January 1.
 
Else if study intervention start date is not missing:
 
 
If year of start date = year of study intervention start date, then 
 
If stop date contains a full date and stop date is earlier than study intervention start date, then set start date = January 1.
 
 
 
 	
 
	Missing start day	
If study intervention start date is missing (i.e., participant did not start study intervention), then set start date = 1st of month.
 
Else if study intervention start date is not missing:
 
 
If month and year of start date = month and year of study intervention start date, then 
 
If stop date contains a full date and stop date is earlier than study intervention start date, then set start date= 1st of month.
 
Else set start date = study intervention start date.
 
 
 
 
Else set start date = 1st of month.
 
In this case, event is considered On-treatment and treatment emergent as per Section 6.3.4.
	Missing start time	
Midnight 0:00:00 will be used for AEs with missing start time to determine if it's AChE-I
 
 
Treatment start time will be used for AEs with missing start time if treatment start date is same as AEs start date.
 
		
If study intervention start date is missing (i.e. participant did not start study intervention), then set start date = January 1.
 
Else if study intervention start date is not missing:
 
 
If year of start date = year of study intervention start date, then 
 
If stop date contains a full date and stop date is earlier than study intervention start date, then set start date = January 1.
 
 
 

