Missing start day	
If study intervention start date is missing (i.e., participant did not start study intervention), then set start date = 1st of month.
 
Else if study intervention start date is not missing:
 
 
If month and year of start date = month and year of study intervention start date, then 
 
If stop date contains a full date and stop date is earlier than study intervention start date, then set start date= 1st of month.
 
Else set start date = study intervention start date.
 
 
 
 
Else set start date = 1st of month.
 
In this case, event is considered On-treatment and treatment emergent as per Section 6.3.4.
						
Missing start time	
Midnight 0:00:00 will be used for AEs with missing start time to determine if it's AChE-I
 
 
Treatment start time will be used for AEs with missing start time if treatment start date is same as AEs start date.
 
						
	
If study intervention start date is missing (i.e. participant did not start study intervention), then set start date = January 1.
 
Else if study intervention start date is not missing:
 
 
If year of start date = year of study intervention start date, then 
 
If stop date contains a full date and stop date is earlier than study intervention start date, then set start date = January 1.
 
 
 
						

Element	Reporting Detail					
		
 
– Else set start date = study intervention start date.
 
 
Else set start date = January 1.
 
In this case, event is considered On-treatment and treatment emergent as per Section 6.3.4.
				
	Missing end day	
Last day (dependent on the month and year example '28/29/30/31') of the month will be used will be used for the day, unless this is after the stop date of study treatment; in this case the study treatment stop date will be used.
				
	Missing end day and month	
No Imputation will be applied in case of AE with missing end day and month
				
	Missing end time	
23:59 will be used for AEs with missing time
				

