	Completely missing start/end date	
 
• Completely missing start or end dates will remain missing, with no imputation applied. Information on AE occurred before, after, or on the same day as the study intervention will be used.
 
• Consequently, time to onset and duration of such events will be missing.
 
• Adverse events with entirely missing or unknown start dates will be assumed to be on-treatment and treatment emergent for reporting.
 
				

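### SAP 4.5.2 and 6.3.4 classify a dosing-day adverse event with no recorded time in opposite ways, because the 6.3.8 imputation rule ties it exactly with first dose

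*SAP*

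**What the plan says.** Three parts of the SAP decide whether an adverse event is treatment-emergent.

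- **SAP 4.5.2 (Adverse Events)** defines a TEAE as an event "with start date/time after the first dose date/time of the study treatment". Its fallback is "If the time part is missing, dates will be considered". If date and time are both missing, it turns to the eCRF question on whether the event came before, after or on the day of study intervention. It then states: "Only TEAE will be included in summary tables, but all AEs will be displayed in detailed subject listings".
- **SAP 6.3.4 (Treatment Emergent Flag)** sets the flag when the event's "onset date/time is on or after treatment start date/time" and writes this out as an inequality that includes equality. Its fallback is "If time is missing, only date will be compared".
- **SAP 6.3.8 (Missing and Partial Dates)** supplies the imputed values. For a missing time on the dosing date: "Treatment start time will be used for AEs with missing start time if treatment start date is same as AEs start date". For a missing start day in the dosing month, or a missing day and month in the dosing year, unless a full stop date precedes dosing: "Else set start date = study intervention start date". Both partial-date rows add that the event counts as treatment-emergent under 6.3.4. The missing-start-time row has no such statement.

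For a wholly missing start date, 6.3.8 says in one bullet that the eCRF timing answer is used, and in another: "Adverse events with entirely missing or unknown start dates will be assumed to be on-treatment and treatment emergent for reporting".

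Protocol 8.4.1 collects adverse events from the start of study intervention and sends occurrences between consent and dosing to medical history. The protocol's own TEAE definition (10.8.4) is in words only and does not settle how a tie is handled.

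**The concern.** At first sight, *after* and *on or after* differ only for an event timed to the minute of first dose, which would hardly ever occur. The imputation rule changes that. It assigns the dosing time to every untimed event on the dosing date, so the tie becomes the standard outcome for a whole class of records, and on that class the two rules disagree.

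Untimed dosing-day events are foreseeable. Under the footnotes to the schedule of activities (Protocol 1.3), the telephone centre that runs Visits 2 to 5 does not ask about adverse events directly and refers spontaneous reports to the site. The planned site safety calls come at Visits 6 and 7, so some first-day onset times may be recalled late. The SAP version history also lists an update to the imputation rules for missing adverse event times, so the sponsor expects some.

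TEAEs are a secondary endpoint. The first dose is taken at the site, and the hours after it are when short-lived gastrointestinal or cholinergic events are plausible. A rule that could leave such events out of every summary table should not depend on which section the programmer reads.

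**Working it through.** **Inputs.** The 4.5.2 rule is event start > first dose. The 6.3.4 rule is event start ≥ first dose. Both compare dates only when time is missing. The 6.3.8 rule sets an untimed dosing-day event to the first-dose time. Planned enrolment is about 90 (Protocol 1.1), used as the approximate size of the safety set. The plan gives no figure on this point to reproduce.

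**Step 1: apply both rules to the possible records.**

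| Record | Start used | TEAE under 4.5.2 | TEAE under 6.3.4 |
|---|---|---|---|
| Dosing day, no time, imputed time | equals first dose | No (not >) | Yes (≥) |
| Dosing day, no time, dates only | same date | No (not >) | Yes (≥) |
| Dosing day, 1 hour after dose | as recorded | Yes | Yes |
| Dosing day, 1 hour before dose | as recorded | No | No |
| Next day, no time | next date | Yes | Yes |

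The sections disagree on the untimed dosing-day event, and they do so whether the programmer uses the imputed time or the date-only fallback. A recorded time equal to the dosing time would also tie, but that is a coincidence.

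**Step 2: see which tied events 6.3.8 protects.** Events with a missing day, or a missing day and month, can also be set to the dosing date. Those rows declare them treatment-emergent under 6.3.4, and 4.5.2 adopts the 6.3.8 rules for partial and wholly missing dates, so they are kept. The missing-start-time row is the one left without that protection.

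**Step 3: size per participant.** Overall TEAE incidence changes only when the lost event is the participant's sole TEAE. The change is then 1/90 = 1.11 percentage points. For a single preferred term, the common-event table in 4.5.2 needs at least 2% before rounding: 2/90 = 2.22% qualifies and 1/90 = 1.11% does not. A term reported by two participants would leave that table if one of them lost her only event under it.

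**Step 4: wholly missing start dates.** Take an event whose eCRF answer is *before*. Under 4.5.2 and the first 6.3.8 bullet it is not treatment-emergent. Under the last 6.3.8 bullet it is. The record is again classified both ways. Section 4.5.2 also does not say which class a same-day answer belongs to.

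**Step 5: apply the correction.** With *on or after* in both sections, the untimed dosing-day event is a TEAE by imputed time and by date alone. An event recorded before dosing stays excluded, and the other rows of the table do not change.

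**The case against.** The strongest reply is that 6.3.4 is the operative rule. It is the section devoted to the flag, it gives an explicit inequality and its own missing-time fallback, and it is the section that 6.3.8 cites when it refers to treatment emergence. A programmer who follows it keeps every untimed dosing-day event. The protocol points the same way: since adverse events are collected only from dosing, one recorded on that date is expected to be post-dose. All adverse events also remain in the listings.

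Much of this stands. It shows that *on or after* is the coherent reading and probably the intended one. It does not remove the conflict, because 4.5.2 is the main-text definition, it controls entry to the tables, and it does not refer to 6.3.4.

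The reply also rules out several stronger readings that a reader might infer:

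- *That these events will be lost and TEAE incidence biased downward.* The documents show a contradiction. Loss follows only if 4.5.2 is programmed literally.
- *That events with a missing day or month are lost too.* The partial-date rows of 6.3.8 expressly keep them.
- *That a total effect of several percentage points can be stated.* The documents give neither the share of participants with a dosing-day event nor the share of such events without a time, and a participant with any other TEAE stays in the overall count.
- *That the wholly-missing-date conflict adds to a downward bias.* The blanket default can only add events. Given the collection window, a *before* answer should be rare.

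**Conclusion.** The SAP contains two rules for the same secondary safety endpoint that disagree on a defined class of records: adverse events on the first-dose date with no recorded time. The disagreement follows from the SAP's own imputation rule and does not need a chance coincidence of times. The supportable size is about 1.1 percentage points of overall TEAE incidence per affected participant with no other TEAE, taking about 90 treated participants, plus the possible loss of a two-participant term from the common-event table. The number of participants affected cannot be known from the documents and may be small or zero.

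The conflict over wholly missing start dates is real and separate. If the default prevails it works in the other direction, by admitting events that the eCRF places before dosing.

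Both are wording conflicts that should be reconciled before the safety tables are produced. They are not evidence that events have been or will be dropped.

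**What to change.** Make three changes to the SAP.

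1. In 4.5.2, replace *after* with *on or after*, or delete the local definition and refer to 6.3.4.
2. In the missing-start-time row of 6.3.8, add the statement already present in the partial-date rows, that the event is treatment-emergent under 6.3.4.
3. For wholly missing start dates in 6.3.8, use the eCRF timing answer where there is one, and apply the treatment-emergent default only when that answer is also missing. State that a same-day answer counts as treatment-emergent, in line with *on or after*.

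The cost is a few sentences, with no new data and no new analyses. Compared with a literal reading of 4.5.2, the first two changes can only keep TEAE counts the same or raise them slightly. Compared with the blanket default, the third can only remove events that the eCRF places before dosing.
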